7.6 Efficacy

The 6-week double-blind Treatment Period will provide the main dataset for inferential analyses.

All efficacy analyses will be performed on the mITT population. Supportive analyses will be performed on the PP population.

The 2 pairwise comparisons of each LX9211 dose levels vs placebo will be performed using Dunnett's test. Testing among the secondary endpoints will not be adjusted for multiplicity, and hence, the analyses will be exploratory. Other endpoints will likewise not be adjusted for multiple testing. Adjusted and unadjusted p-values will be presented.

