10.1 Determination of Sample Size

Proposed Sample Size

A sample size of 75 patients per treatment group who complete the 6-week double-blind Treatment Period will yield 80% power to detect a true mean difference of 1 unit between at least 1 of LX9211 treatment groups and placebo in ADPS change from Baseline, assuming a common standard deviation of 2 and an overall significance level of α=0.05 (2-sided Dunnett's test). Accounting for a dropout rate of 20%, a total of 282 patients (94 patients per treatment group) will be enrolled and randomly assigned to treatment in a 1:1:1 ratio. This sample size is adjusted for the multiple comparisons of each LX9211 treatment group with placebo (Westfall, 1999).

Sample Size Reestimation

Due to the uncertainty in the outcome for the primary endpoint analysis secondary to potential variations in some of the key design parameters such as the dropout rate and standard deviation associated with the targeted treatment group difference, an unblinded SSR adaptation will be implemented at the time of the interim analysis testing for futility. This will occur when the first 141 patients have been accrued and followed thru Week 6 or dropped out early from the trial (whichever event happens first). Should a patient drop out early in the study, but return for the Week 6 visit, the Week 6 data will be used in the analysis. The Chen-DeMets-Lan method will be used for the unblinded SSR since it requires minimal change from a group sequential test. This method requires specification for a number of criteria related to the allowable conditions for increasing the sample size that ensures that ordinary group sequential methods can be applied while seeing that the overall error is not inflated compared to the original group sequential design. The 2 primary conditions which are required and satisfied in the SSR for this study are that (a) the SSR is made at the penultimate look, and (b) the conditional power at the penultimate look occurs between 50% and 80.3% (the original specified power under the group sequential design). The SSR is linked to the projected effect size falling within this "promising" or "favorable" range of conditional power. Having satisfied these 2 main conditions, the Type I error rate after increasing the sample size until the conditional power equals the original target power will not be greater than the Type I error from the originally proposed design.

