2.3 Sample Size and Power

A sample size of 75 patients per treatment group who complete the 6-week double-blind Treatment Period will yield 80% power to detect a true mean difference of 1 unit between at least 1 of LX9211 treatment groups and placebo in ADPS change from Baseline, assuming a common standard deviation of 2 and an overall significance level of $\alpha=0.05$ (2-sided Dunnett's test). Accounting for a dropout rate of 20%, a total of 282 patients (94 patients per treatment group; 75 patients $\times 1/(1-0.20)$) will be enrolled and randomly assigned to treatment in a 1:1:1 ratio. This sample size is adjusted for the multiple comparisons of each LX9211 treatment group with placebo ([Westfall, 1999](#)).

Sample Size Reestimation

Due to the uncertainty in the outcome for the primary endpoint analysis secondary to potential variations in some of the key design parameters such as the dropout rate and standard deviation associated with the targeted treatment group

CONFIDENTIAL

Document Date: 07JUN2022

Page 11 of 55

ST-AD-008 version 05

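### Step-down Dunnett would be a cheap improvement on the planned single-step test of the two doses: same 0.05 family-wise error, and a better chance of establishing both doses if both work

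*SAP*

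**What the plan says.** SAP 7.6 and the Multiplicity paragraph of Protocol 10.4.2.2 carry the same rule: "The 2 pairwise comparisons of each LX9211 dose levels vs placebo will be performed using Dunnett's test". Both then leave secondary and other endpoints unadjusted and add: "Adjusted and unadjusted p-values will be presented". Neither names a step-down, closed or hierarchical order, and neither says what the unadjusted p-values are for.

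The sample size in Protocol 10.1, repeated in SAP 2.3, rests on the same test at an overall two-sided alpha of 0.05: "A sample size of 75 patients per treatment group who complete the 6-week double-blind Treatment Period will yield 80% power", the target being "to detect a true mean difference of 1 unit between at least 1 of LX9211 treatment groups and placebo in ADPS change from Baseline". The SD is taken as 2 in every arm. Allowing for 20% dropout, "a total of 282 patients (94 patients per treatment group) will be enrolled and randomly assigned to treatment in a 1:1:1 ratio".

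SAP 7.6.1 asks for p-values and 95% confidence intervals for each dose-placebo difference and does not say that the intervals are simultaneous. The interim futility boundary (Protocol 10.4.5.7, SAP 7.8) uses a one-sided per-comparison error of 0.0141. Sample size re-estimation (Protocol 10.1, SAP 2.3) depends on conditional power between 50% and 80.3%.

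**The concern.** The primary family has two hypotheses. Once one has been rejected, only one remains, and by closed testing it can be tested at the full two-sided 0.05 without exceeding the family-wise rate. Dunnett's test in its ordinary single-step form does not use this: the second dose still faces the multiplicity-adjusted threshold.

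The difference shows in one situation. Suppose one dose is clearly significant and the other has a nominal two-sided p between 0.027 and 0.05. The plan as written must call the second dose not significant; a step-down rule would establish it at the same overall alpha. In a trial that compares two doses with placebo, that is a conclusion worth having if it costs nothing in family-wise error.

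**Working it through.** **Inputs.** From Protocol 10.1 and SAP 2.3: 75 completers per arm, difference 1, SD 2, 1:1:1 allocation, overall two-sided alpha 0.05. Equal arms give a correlation of 0.5 between the two contrasts; df = 3 × 75 − 3 = 222. The documents give no effect for the second dose, so it is an assumption and is varied below.

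**Reproducing the plan.**
- Noncentrality: 1 / (2 × √(2/75)) = 3.062.
- Two-sided Dunnett critical value, two comparisons, 222 df, by numerical integration: 2.226 (nominal p 0.0270).
- Power for one dose with effect 1: about Φ(3.062 − 2.226) = Φ(0.836) = 0.798, and 79.8% by simulation. Stated: 80%.
- 75 / (1 − 0.20) = 93.75, rounded up to 94; 3 × 94 = 282, as stated.

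**The two rules.** Single-step: each |t| is compared with 2.226. Step-down: the larger |t| is compared with 2.226; if it exceeds that, the smaller is compared with 1.971, the ordinary 0.05 value for 222 df. The first step is the same, so the chance of at least one rejection cannot differ.

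**Chance of establishing both doses** (at least 1.5 million simulated trials per scenario, so Monte Carlo standard error at most √(0.25/1,500,000) = 0.0004):

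| True effects | Single-step | Step-down |
|---|---|---|
| 1 and 1 | 68.5% | 76.9% |
| 0.75 and 1 | 48% | 58% |
| 0.75 and 0.75 | 36.4% | 46.0% |
| 0.5 and 1 | 23% | 32% |

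With both effects 1, the chance of at least one rejection is 91.1% under either rule. Power for a given dose is then half the sum of the chances of at least one and of both: (91.1 + 68.5)/2 = 79.8% single-step, (91.1 + 76.9)/2 = 84.0% step-down. With 94 completers per arm (no dropout) the chance of both goes from 81.0% to 87.2%.

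**If only one dose works** (effects 1 and 0). Power for the working dose is P(at least one) + P(both) − P(null dose rejected):
- single-step: 0.8070 + 0.0178 − 0.0270 = 0.7978;
- step-down: 0.8070 + 0.0354 − 0.0431 = 0.7993.

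So there is no true-positive gain of any practical size.

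**Error.** If both doses are null, a false rejection needs the first step, so the family-wise error is 0.050 as before. If one dose is null, rejecting it needs at least |t| > 1.971, which has probability at most 0.050. With the other dose at effect 1, the null dose is rejected with probability 0.027 single-step and 0.043 step-down.

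**The case against.** The planned test is valid, and the analysis agrees with the sample size calculation. The trial is powered for at least one dose, and on that criterion the two rules are identical; the documents set no target for establishing both. It is a Phase 2 trial. Step-down also has a price: with one working dose, an ineffective second dose is declared effective more often (0.043 against 0.027). Single-step Dunnett has matching simultaneous intervals, whereas after step-down such an interval can include zero for a dose established at the second step. The interim rules are written around a per-comparison threshold.

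Most of this stands, and it makes the point an improvement rather than a defect. It does not remove the point. The extra false rejections stay within the family-wise limit that the plan chose. The SAP does not say that its 95% intervals are simultaneous, and an ordinary 95% interval agrees with the second-step test. The futility boundary is non-binding. Conditional power of at least 50% against the stricter critical value is also at least 50% against the looser one for the same comparison. The interim text needs a sentence, not a redesign.

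A reader might infer that tabulating unadjusted p-values lets the primary comparisons be decided on them, with inflated family-wise error. The documents do not support this. Dunnett's test at overall 0.05 is the only rule given for the primary family, and the sentence on unadjusted p-values directly follows the statements that secondary and other endpoints are not adjusted. What is missing is only a line on their role.

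**Conclusion.** A worthwhile, inexpensive improvement to a valid plan. Step-down Dunnett rejects everything that single-step Dunnett rejects and sometimes the second dose as well, at the same 0.05 family-wise error and with the same chance of at least one rejection.

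The gain is conditional. The rise from about 68% to 77% requires a true 1-unit effect in both doses, 75 completers per arm and SD 2. In the other scenarios checked with both doses active, the gain is about 8 to 10 percentage points. With one active dose there is essentially none, and the false-rejection rate for the other dose rises from 0.027 to about 0.043, at most 0.050. A reader might take 68% as a shortfall against the stated 80%. It is not: the 80% is the power for a single comparison, and the plan makes no claim about both.

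That the plan means single-step Dunnett is inferred from the ordinary meaning of the test and the absence of any order. The sample size agrees with that reading but would not by itself exclude step-down, since with one active dose both rules give about 80%. The figures are for a fixed sample and do not include the possible increase to 351 patients.

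**What to change.** Before unblinding, amend SAP 7.6 and the Multiplicity paragraph of Protocol 10.4.2.2:

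- Name step-down Dunnett for the two primary comparisons. The dose with the smaller p-value is tested on its Dunnett-adjusted two-sided p at 0.05. Only if that is significant, the other dose is tested on its unadjusted two-sided p at 0.05. The order comes from the data and is not a fixed dose sequence.
- Report the adjusted p for the second dose as the larger of the first dose's Dunnett-adjusted p and the second dose's unadjusted p.
- State that, for the primary comparisons, unadjusted p-values have no role outside the second step.
- Add a footnote that any simultaneous Dunnett interval may include zero for a dose established at the second step, and record the change in false-rejection risk for an inactive second dose.
- In Protocol 10.1 and 10.4.5.7 and SAP 2.3 and 7.8, add a sentence that the futility boundary and conditional power continue to use the first-step per-comparison critical value.

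The cost is about a paragraph in each document plus the interim sentence. Both p-values are already planned output; sample size and stated power do not change. If the sponsor prefers to keep single-step Dunnett, the sentence on the role of the unadjusted p-values is still worth adding, worded to say that they decide nothing in the primary comparisons.

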7.6.1 Primary Efficacy Analysis

The primary endpoint is the change from Baseline to Week 6 in ADPS, based on Question 5 of the BPI-DPN, the 11-point scale (0 [no pain] to 10 [pain as bad as you can imagine]). The primary analysis will be based on observed data including data measured after the initiation of rescue medications.

Baseline is defined as the average of the Week 2 Run-in Period data collected by patients in the daily pain diary, provided that ≥ 5 days from that period are available for analysis. The post-Baseline values will be calculated by week as the mean value of the Question 5 for ADPS of the BPI-DPN, rated by patients each evening and collected during the target week period. A minimum of 4 non-missing data within the target week period is required for the calculation. The change from

Baseline values at post-Baseline weeks will be calculated as the absolute difference between the Baseline value and post-Baseline values, ie

$$\text{change from Baseline} = \text{post-Baseline value} - \text{Baseline value}$$

The ADPS calculated for each post-Baseline week until Week 6, and the change from Baseline in ADPS at post-Baseline weeks until Week 6 will be summarized by Week using standard descriptive statistics. Data from all study visits, scheduled and unscheduled, and from the daily pain diary will be listed.

A restricted maximum likelihood-based, MMRM approach will be used to assess the difference between LX9211 and placebo in the primary endpoint (ie, change from Baseline to Week 6 in the ADPS derived from data collected daily from Question 5 of the BPI-DPN instrument). The MMRM model will include fixed effects of treatment, week, treatment-by-week interaction, the randomization stratum of Baseline pain severity (moderate, severe), and Baseline ADPS score as a covariate. An unstructured covariance structure will be used to model the within-patient error. Other covariance structures will be explored should convergence not be met. The Kenward-Roger approximation will be used to estimate the denominator degrees of freedom.

The adjusted mean change in ADPS from baseline to Week 6 for each treatment group and the 95% confidence intervals (CIs) will be estimated in the framework of this model, as well as the between-group differences (comparing each LX9211 treatment group to placebo) and the 95% CIs for the difference.

Summarization of the inferential statistics will include the Least Squares means (LS means), standard error (SE) of the estimates, p-values, and 2-sided 95% CIs. These statistics will be provided for the within treatment group changes from Baseline and for the comparison of each dose level of LX9211 (100 mg/10 mg or 200 mg/20 mg) versus placebo for the change from Baseline scores. Tabulation of the inferential results (CIs and p-values) will include the observed finds from the statistical model.

The same analysis will be performed using the PP population.

Figures displaying the arithmetic mean change from Baseline in ADPS by week as well as LS mean change by week, including Week 6, will be presented by treatment group for the mITT population.

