10.4.2.1 Analysis of primary efficacy endpoint

The primary endpoint is the change from Baseline to Week 6 in ADPS. The primary analysis will be based on observed data including data measured after the initiation of the rescue medications.

A restricted maximum likelihood-based, mixed-effects model repeated measures (MMRM) approach will be used to assess the difference between LX9211 and placebo in the primary endpoint (ie, change from Baseline to Week 6 in the ADPS derived from data collected daily from Question 5 of the BPI-DPN instrument). The MMRM model will include fixed effects of treatment, week, treatment-by-week interaction, the randomization stratum of Baseline pain severity, and the Baseline score as covariate. An unstructured covariance structure will be used to model the within-patient error. The Kenward-Roger approximation will be used to estimate the denominator degrees of freedom. Other covariance structures will be explored should convergence not be met. In the event that a rescue medication is used, a supplementary MMRM model will be applied to a dataset that excludes data collected after the initiation of the rescue medication. To assess the robustness of the MMRM analyses performed under the missing at random (MAR) assumption, and given the long half-life of LX9211, pattern mixture models (PMM) with copy reference-based imputation methods will be applied to both datasets (with and without data collected after the initiation of the rescue medication). The imputed datasets will be combined by use of Rubin's rule and analyzed using an analysis of covariance (ANCOVA) model fitted for the fixed effects of treatment, the randomization stratum of Baseline pain severity, and the continuous fixed covariate of Baseline score.

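### Optional improvement: let the Baseline ADPS slope differ by week in the primary MMRM, because nothing in the plan supports one slope for Weeks 1 to 6

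*SAP*

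**What the plan says.** SAP 7.6.1 names the target: "The primary endpoint is the change from Baseline to Week 6 in ADPS". On the fixed effects it says: "The MMRM model will include fixed effects of treatment, week, treatment-by-week interaction". From the interaction on, the list reads: "treatment-by-week interaction, the randomization stratum of Baseline pain severity (moderate, severe), and Baseline ADPS score as a covariate". Protocol 10.4.2.1 ends its list in the same way: "the randomization stratum of Baseline pain severity, and the Baseline score as covariate". For the covariance the SAP says: "An unstructured covariance structure will be used to model the within-patient error". Week interacts only with treatment; neither document has a Baseline-by-week term.

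Three other places bear on this:

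- SAP 7.6.2 and 7.6.2.3 apply a similar MMRM to the BPI-DPN scores, with visit in place of week for the clinic items and the item's own Baseline value as covariate.
- SAP 7.6.3 ends the pattern-mixture analysis in an ANCOVA at Week 6 only, so that sensitivity analysis has its own Week 6 Baseline slope.
- SAP 8, on changes in planned analysis, concerns only the NPSI and leaves the primary model as it is.

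**The concern.** The model is flexible everywhere except in the Baseline adjustment. Any two post-Baseline weeks may correlate freely, but Baseline must predict change equally well in all six weeks. Baseline is the diary mean over Days -7 to -1 (SAP 6.1.1), adjacent to Week 1 and five weeks before Week 6. If its predictive slope falls over that time, the common slope is a compromise across weeks and fits Week 6 less well than a slope of its own.

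Two things are at stake, both conditional. The Week 6 contrast may carry residual variance that one extra term would remove. And if dropout depends on Baseline differently by arm, a misfitted slope can shift the Week 6 estimate slightly.

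**Working it through.** **1. The two models.** In the plan, mean change = week + arm-by-week + stratum + b × Baseline. The alternative replaces b by a separate slope for each week. That is 6 slopes instead of 1, so 6 - 1 = 5 extra parameters. The clinic-visit BPI-DPN items have three post-Baseline visits through Week 6 (Weeks 2, 4 and 6), so the cost there is 3 - 1 = 2.

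**2. The plan's own figure.** Inputs from SAP 2.3: difference 1, SD 2, 75 completers per arm, 80% power, 20% dropout. Input from SAP 7.8: one-sided 0.0141 per comparison (z = 2.1945).

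- n per arm = 2 × (2.1945 + 0.8416)² × 2² / 1² = 73.7, so 74 (stated: 75).
- Power at 75: 1 / (2 × √(2/75)) = 3.062, and 3.062 - 2.1945 = 0.867, which gives 80.7%. With the exact Dunnett critical value 2.226 it is 79.8%.
- 75 / 0.80 = 93.75, so 94 per arm, and 3 × 94 = 282.

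The stated figures reproduce. They rest on an SD of 2 with no Baseline adjustment, so the choice of slope does not affect them.

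**3. Precision.** The SAP model was simulated with 282 patients allocated 1:1:1, REML, unstructured 6 × 6 covariance, about 20% monotone dropout, a Week 6 difference of -1, and 800 datasets per scenario with two dose comparisons each. Each dataset was fitted both ways. Kenward-Roger was not available, so 2.226 was used for both models. The following are assumptions, not taken from the documents: Baseline mean 6.6 and SD 0.9 or 1.2, truncated to 4.5-9.5; residual SD rising from 1.1 to about 2; adjacent-week correlation 0.6 or 0.85; linear slope decline. Here slope means the slope of the weekly score on Baseline.

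Change in effective sample size = (SE common / SE by-week)² - 1. The SEs shown are for Baseline SD 1.2 and correlation 0.85; the percentages use unrounded SEs.

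| Slope, Week 1 to Week 6 | SE common | SE by-week | Effective N, this setting | Range over settings |
|---|---|---|---|---|
| 0.8 throughout | 0.3097 | 0.3101 | -0.3% | -0.3% |
| 0.9 to 0.7 | 0.3086 | 0.3075 | +0.7% | +0.3% to +0.7% |
| 0.95 to 0.5 | 0.3064 | 0.2992 | +4.8% | +2.9% to +4.8% |
| 1.0 to 0.3 (extreme) | 0.3039 | 0.2863 | +12.7% | +8% to +13% |

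For the moderate decline, power rose by 0.1 to 2.0 points. A second simulation with 94 per arm gave variance ratios, common to by-week, of 0.995-1.000 for equal slopes, with a gain of about 1% for mild and about 7% for moderate decline. Together the two give roughly 0-1% for mild and 3-7% for moderate decline. On 282 patients, 0.3% is 0.8 of a patient, 3% is about 8 and 7% is about 20.

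**4. Shift in the estimate.** In the simulation of step 3, the mean Week 6 difference agreed between the two models to within 0.003, also when dropout depended on the previous week's score. With dropout depending on Baseline on active only, the estimates differed by about 0.02-0.07 points for mild to moderate decline. With equal slopes there was no shift. Against an SE of about 0.31, this is 0.02/0.31 = 0.06 to 0.07/0.31 = 0.23 of an SE.

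**The case against.** The case for leaving the model alone is a fair one. The model is complete, prespecified and the same in both documents. No stated power, sample size or Type I error figure depends on the missing term. The gain needs a real decline in slope; with a mild decline it is trivial. The shift needs arm-specific, Baseline-dependent dropout, whereas the protocol synopsis assumes a uniform 20% rate. The Week 6 ANCOVA in SAP 7.6.3 already has a Week 6 slope. The BPI-DPN analyses are exploratory (SAP 7.6).

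Most of this stands, and it is why the point is a suggestion. Two parts do not settle it. The ANCOVA rests on placebo-based imputation, so it is not a like-for-like check: if it differs from the primary result, the missing-data assumption and the Baseline adjustment are mixed. And the plan gives no reason to expect equal slopes, while guarding against unequal ones costs almost nothing.

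It may also be said that the severity stratum, taken from the same run-in diary, is likewise a main effect only. That is correct. A stratum-by-week term follows the same logic, but its separate effect was not sized here.

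A reader might infer that pain is known to track Baseline less over time, so that the gain is certain. The documents contain no Baseline-to-week correlations and say nothing on this; the decline is an assumption.

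**Conclusion.** This is a cheap improvement to the primary model, not an error in it. If the slopes are equal, the extra term costs about 0.3% of effective sample size (at most 0.5% in either simulation). If they decline, it gains roughly 0-1% in Week 6 variance for 0.9 to 0.7 and about 3-7% for 0.95 to 0.5. It removes a shift of about 0.02-0.07 points only where slopes differ and dropout depends on Baseline differently by arm. All gains rest on the assumed values above, chiefly a Baseline SD of about 1.2 and about 20% dropout.

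A reader might go further and conclude that the planned analysis is biased or the trial underpowered. The documents do not support that. The design figures reproduce without any Baseline adjustment, and the two models gave the same Week 6 estimate unless dropout was tied to Baseline differently by arm. Nor is the term strictly free: it spends 5 df.

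**What to change.** Before unblinding:

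- In SAP 7.6.1, add a Baseline ADPS-by-week term to the primary MMRM and leave the rest of the model unchanged.
- In SAP 7.6.2.3, add Baseline-by-visit for the clinic-visit BPI-DPN items and Baseline-by-week for the diary sleep item.
- Record the difference from protocol 10.4.2.1 in SAP 8.

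If the primary model can no longer be changed, prespecify the by-week model as a sensitivity analysis.

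The cost is 5 df in the primary model and 2 df for clinic-visit items through Week 6. No new data are needed, and the sample size does not change.
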